- 2) **Neuroscores** (as previously described)[31-33] will be assigned at each visit by [name] as per her clinical routine. The SWS neuroscore is comprised the frequency of seizures, extent of hemiparesis, assessment of visual field cut, and degree of cognitive functioning with a total score of 15 possible points. Neurologic exam and general physical exam will also be performed remotely at each visit. (Routine care)
- 3) Participants will be asked at each remote visit about any change in neurologic symptoms. (Routine care)
- 4) For subjects with a facial port-wine birthmark, frontal and profile photograph will be taken under standardized conditions with scoring of the port-wine birthmark (**Port-wine birthmark score**) for percent of face covered, thickness of birthmark, and darkness of birthmark color. Families will be mailed a color chart (see appendix) to hold up next to the subject while photos are being taken. Subjects without any facial port-wine birthmark will only need photographs taken at a single visit to confirm the lack of birthmark. (Research, See Study Visit Table).

Table of Remote Visits	Screening	Baseline	Core	e Phase	Endpoint 6 months		
Visit Number	1	2	3	4	5		
Study Week	-2 ± 14	days 0	4	12 ± 7 days	24 >		
Consent	х						
Physical Exam	Х	Х	Х	Х	Х		
Neuroscore	Х	х	Х	Х	X		
Neuro QoL	Х	Х	Х	Х	Х		
Incl/Excl Criteria	Х	Х	Х	Х	Х		
Past Medical	х						
History Diagnosis of SWS	Х						
Seizure Hx	X	Х	X	X	X		
Previous AED Hx	X				^		
Current Med Hx	Х	х	Х	Х	Х		
Picture Taken		Х			Х		
Rescue Meds	Х	Х	Х	X	Х		
AEDs	Х	Х	Х	Х	Х		
Motor, NP, psychiatric Assessments	<				X ± 7 days		
Labwork							
AED Levels CMP (renal, hepatic)	X		X	X	X X		
CBC	Х		Х	X	Х		
CBD/THC Ratio			Х	X	X		
Urinalysis	Х		Х	X	X		
Pregnancy Test (if applicable)	Х		Х	Х	Х		
Safety							
Adverse Events check		X	X	X	Х		
Safety Calls:		←		Bi-monthly			
Continue or Remove?	х	х	Х	Х	Х		
Patient Reported Outcomes			Х	х	Х		

- 5) CBC, LFT, BUN, creatinine levels, electrolytes, and urinalysis will be measured at each visit (screening, 1, 3, and 6 months on drug). Concomitant AED plasma concentrations will be measured at the same visits. CBD/THC ratio in urine will be measured three times; at the one month visit, at the three month visit, and at the 6 month visit. All lab tests will be done remotely at a site local to the participant and charged to the study budget.

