- 6) hCG urine pregnancy test will be used for all female participants Tanner stage 2 and above (see Study Visit Table). We will tell subjects that they must be using effective birth control (for example, abstinence, birth control pills, contraceptive implants, condoms) and confirm that this is the case at each study visit. We will inform female subjects that they should not become pregnant or breastfeed a baby while on this study or for 12 weeks after taking Cannabidiol. We will also inform male subjects that they should not get their partners pregnant while on this study or for 12 weeks after taking Cannabidiol. Anyone who becomes pregnant while on the study will be removed immediately.

Case Report Forms: Forms generated for use as case report forms will also be used as source documents. Forms will be filled out during the study visit with data. Immediately after the visit, the form will be photocopied and one copy will immediately have the study subject ID# written on it (case report form). The other copy will immediately have the subject name written on it (source document).

b. Study duration and number of study visits required of research participants.

Duration of therapy: Study duration for subjects will be between 6 months to 2 years depending on the age at enrollment. During the study, subjects will be seen at 1 month, 3 months and the every 3 months until they are 2 years of age. Therefore the number of study visits will range from 4 to 8, again depending on the age at enrollment. Total length of study for completion of all subjects will be 4 years as outlined in the Milestones Table attached. Once the optimal dose is found (20 mg/kg/day or maximal tolerated dose; expected to be reached within 4 weeks), participants will continue on the Core Phase until 2 years of age. At the end of the core phase, cognitive and all other testing will be repeated. **Total duration for each subject= until 2 years of age, a minimum of 6 months and 5 visits.**

Study Visit 1: Screening Visit- Informed consent process, eligibility criteria reviewed. The following tests are done at *visit one*, *or at or before visit 2* (maximum of two weeks between visits 1 and 2): baseline developmental testing, baseline labs sent, neurological exam, and baseline motor testing, Quality of life measures, motor testing video, Neuroscore and Port-wine birthmark score.

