Study Visit 2: Baseline Visit- Confirm eligibility and begin drug at dose 1 (see Visit Table and Dose Schedule). Provide study drug dosing record and instruct on use. History, exam, Quality of life measurs, have picture taken, and Port-wine birthmark score.

During visits 3 and beyond (see Visit Table)- the participants will undergo clinical neurologic assessments, blood draws for laboratory tests, study drug accountability, concomitant medication survey, adverse event reporting, and study drug administration (see Visit Table for details). Also, Quality of life measures and neuroscore.

Final Study Visit- Repeat all assessments- developmental testing, labs, neurological exam, motor testing, Quality of life measures, motor testing video, Neuroscore, have picture taken, and Port-wine birthmark score. Determine whether subject will continue on Epidiolex or will be weaned off.

Clinical Follow Up: Subject will be seen one month later for clinical follow up whether on or off Epidiolex.

An additional blood draw will also be necessary within 72 hours of a previous blood draw if the most recent result indicates a clinically significant (>3xULN) elevation of ALT or AST. At minimum, the following tests will be repeated: ALT/AST, total bilirubin, and alkaline phosphatase. A GGT test will also be performed at that time. This bloodwork (ALT/AST, total bilirubin, and alkaline phosphatase and GGT test) will also be necessary if: 1) the dose of the study drug dose is increased after the escalation phase, 2) another drug which affects liver function is added, stopped, or has a dose change, or 3) the subject has one or more of the following symptoms without another explanation: fatigue, encephalopathy, nausea, vomiting, right upper quadrant pain or tenderness, abdominal pain or distension, fever, excessive bruising, excessive nose or gum bleeds, or petechia. All trial subjects with elevated LFTs will be followed closely until all abnormalities return to the baseline state as assessed by the investigator with AST/ALT < 3x ULN and will be followed until ALT/AST have normalized and symptoms resolve.

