Those who do not demonstrate a clear benefit after six months of treatment will be weaned off of the study drug over a month, and seen back for one final follow-up visit one month later. All subjects removed early from the study will be requested to complete the end of study assessments while still on study drug; but only if safely possible and with subject consent.

At study's end, any patient doing well on Epidiolex and demonstrating improvement on cognitive, neurologic, mood and/or behavioral assessments may continue on the drug (extension study). Every effort will be made to obtain insurance authorization based on the cognitive and medical improvements

demonstrated by the trial; if required the drug will be provided free of cost to the subject until the drug is approved for clinical use for the treatment of cognitive impairments (or other measured indications) in patients with Sturge-Weber syndrome.

They will then be followed and seen about every 3 months, at which time interim history, including evaluation of side effects and patient reported outcomes, neuroscore, photographs of the port wine birthmark, and the Neuroquality of Life questionnaire will be collected. During the extension phase, the PI will have the ability to change dose (increase and decrease) dose of Epidiolex and other anti-seizure medications as clinically indicated. The maximum dose of Epidiolex will not exceed 20 mg/kg/day. The extension study will consist of at least 4 visits, with the option to remain on the extension study until insurance company approval is obtained for Epidiolex. Study drug will be provided by Greenwich Biosciences until insurance coverage is obtained. The study coordinator will contact the family once per month to ensure the subject is taking the Epidiolex. The study coordinator will ask how much of the Epidiolex the subject has remaining and will ask to see the bottle(s) to confirm.

Lab work (CBC, anticonvulsant levels, and chemistries about every 3 months) will be done as part of clinical care. At all extension study visits, there will be a urine pregnancy test. If the subject is under the age of 18, these results will be given to the parents.

Every six months, an interim analysis will be done of adverse events and outcome measures. Results will be discussed by the Research Investigators and a summary sent to Greenwich Biosciences.

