- 2. Patients who have had a major surgery or significant traumatic injury within 4 weeks of study entry, patients who have not recovered from the side effects of any major surgery (defined as requiring general anesthesia), or patients that may require major surgery during the course of the study.
- 3. Patients who start or discontinue a seizure, mood or behavioral medication in the 4 weeks leading up to screening.
- 4. Prior treatment with any investigational drug or use of any other cannabis product within the preceding 4 weeks prior to study entry.
- 5. Patients with a history of non-compliance to medical regimens or who are considered potentially unreliable or will not be able to complete the entire study. This includes those in foster care, or those unable to keep follow-up appointments, maintain close contact with Principal Investigator, or complete all necessary studies to maintain safety.
- 6. Pregnant or nursing (lactating) women, where pregnancy is defined as the state of a female after conception and until the termination of gestation, confirmed by a positive hCG laboratory test.

6. Drugs/ Substances/ Devices

a. The rationale for choosing the drug and dose or for choosing the device to be used.

Epidiolex is a pharmaceutical grade purified version of cannabidiol which has been extensively studied in many *in vivo* and *in vitro* models. [name] has previously studied use of Epidiolex in Sturge-Weber patients with medically refractory seizures. 3 of the 5 patients in this cohort had sustained improvement in their seizures, with one patient achieving seizure freedom. Of interest, these patients and their families also noted cognitive, mood, and behavior improvements.[1] Other studies suggest anti-depressant like effects,[34] and reduced social anxiety symptoms[35] associated with Cannabidiol use. In addition, other studies suggest cannabidiol has neuroprotective benefit,[36] effects on abnormal angiogenesis,[37] and anti-inflammatory effects;[38] these effects would be expected to be beneficial in SWS.

b. Justification and safety information if FDA approved drugs will be administered for non-FDA approved indications or if doses or routes of administration or participant populations are changed.

Epidiolex is currently FDA approved only for treatment of medically refractory seizures in Lennox-Gastaut syndrome, Dravet syndrome with a dose range of 5-20 mg/kg/day. It is no longer a scheduled drug.

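### The only pregnancy test scheduled before dosing is at screening, so it can be 14 days old at first dose, or about 21 if mailed drug arrives a week after Visit 2

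*Combined protocol and SAP*

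**What the plan says.** Section 4a, Laboratory tests and clinical procedures, item 6, defines who is tested and refers to the visit table for when: "hCG urine pregnancy test will be used for all female participants Tanner stage 2 and above (see Study Visit Table". In the Table of Remote Visits, the row "Pregnancy Test (if applicable" is marked at screening (Visit 1) and at Visits 3, 4 and 5. The baseline cell (Visit 2) is empty. The row "Incl/Excl Criteria" is marked at every visit, including Visit 2.

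Section 4b describes Visit 2 as the point to "Confirm eligibility and begin drug at dose 1". Its list of Visit 2 procedures names no pregnancy test. For Visit 1, section 4b allows a "maximum of two weeks between visits 1 and 2" and lets the baseline labs be sent at any point up to Visit 2. hCG is not named in that list.

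The Study Overview in section 4a has the drug posted to the home, with shipping inside a week of a prescription whose date is not given. The coordinator confirms that it has arrived. No test is tied to that contact.

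Exclusion criterion 6 in section 5 defines pregnancy as "confirmed by a positive hCG laboratory test". Item 6 also requires effective contraception, which staff must "confirm that this is the case at each study visit". For the extension phase, section 4g states: "At all extension study visits, there will be a urine pregnancy test".

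**The concern.** The plan rechecks a test-defined exclusion at Visit 2 without a new test. Among Visits 1 to 5 and the extension visits, the visit that begins exposure is the only one with no pregnancy test. The eligibility decision on pregnancy therefore rests on the screening result, however old it is by the first dose.

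What is at stake is fetal exposure. Section 8a describes the effects of cannabidiol on an embryo or fetus as unknown, and section 8b tells participants that serious harm is possible. The next scheduled test is about a month into treatment, after the weekly titration has reached 20 mg/kg/day at week 3. A pre-dose test can prevent exposure altogether. A test on treatment can only shorten it.

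**Working it through.** The plan states no figure for the age of the test at first dose, so there is none to reproduce. The check is a day count.

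**Is the blank Visit 2 cell real?** The table was read by a program, so a lost mark is possible. Two things argue against it. The CBC and urinalysis rows show the same pattern, marked at screening and Visits 3 to 5 and blank at Visit 2. Item 5 in section 4a also lists laboratory tests at screening and at 1, 3 and 6 months on drug, with no baseline draw. The general lab-work paragraph in section 4a speaks of labs at each visit, but hCG is not among the tests it names.

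**Inputs**
- g = days from Visit 1 to Visit 2: 0 to 14 (cap in section 4b).
- d = days from Visit 2 to first dose: not stated. I assume 0 (drug in hand at Visit 2) to 7 (prescription written at Visit 2 and delivery taking a week, from the shipping time in the Study Overview).

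**Age of the screening test at first dose, if done at Visit 1** = g + d
- Cap, drug in hand at Visit 2: 14 + 0 = 14 days.
- Cap, delivery a week after Visit 2: 14 + 7 = 21 days.

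**If hCG is done with the baseline labs on the day of Visit 2**, which is not required: 0 + 0 = 0 days to 0 + 7 = 7 days.

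**With an added test**
- At Visit 2: the age is d, so 0 to 7 days.
- At drug receipt, just before the first dose: about 0 days.

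**What the added test gains.** Let L be the test's detection delay, S the day of the screening test and F the day of first dose. A test on day T misses conceptions between T − L and T. Moving the last pre-dose test from S to F makes conceptions between S − L and F − L detectable. That is a window of F − S days, so 14 or 21 days in the two capped cases, whatever the value of L. Conceptions in the final L days before first dose stay undetected under either schedule.

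**Number affected.** The anticipated-enrollment table in section 4a plans 5 females among 10 participants. Ages run from 3 to 50 and Tanner stage is not given, so between 0 and 5 of those planned would need the test.

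**The case against.** The best defense is that the blank is deliberate. The trial is remote and uses outside laboratories, so the screening labs serve as the baseline labs for every analyte. The two-week cap keeps them recent, and urine hCG would naturally be collected with the urinalysis, possibly close to Visit 2. The plan sets no maximum age for a pre-dose pregnancy test, so a result up to 14 days old breaks no stated rule. Contraception is mandatory and confirmed at Visit 2, and a pregnancy leads to immediate removal. On treatment, the plan already accepts 8 weeks (week 4 to 12) and 12 weeks (week 12 to 24) between tests.

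Much of this stands, and it makes the gap a residual one. It does not close it. Collecting hCG with the baseline labs is possible but not required. Confirmation of contraception is a report, and it cannot reveal a pregnancy that has already begun. The longer on-treatment intervals do not settle the matter, because the pre-dose test serves a different purpose: it is the eligibility check.

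Three stronger readings are tempting.
- A reader might infer from the table's screening window, week −2 ± 14 days, that the test could be 14 + 14 = 28 days old at Visit 2. The explicit cap in section 4b contradicts that, and the cap is the safer basis.
- A reader might multiply the gap by a pregnancy rate to get an expected number of conceptions. No document gives such a rate, and, as shown above, conceptions in the gap are not the same set as those the added test would detect.
- A reader might infer that Study Week 0 must be redefined as the first-dose date because the drug is mailed. That is unnecessary, since the text already times follow-up by months on drug.

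**Conclusion.** The gap is real, and closing it is a worthwhile but modest safety improvement. Followed exactly, the plan allows the first dose on a pregnancy result up to 14 days old. The figure becomes about 21 days if the mailed drug arrives a week after Visit 2. The 14-day figure rests on the section 4b cap. The extra 7 days rest on an assumption about when the prescription is written and how long delivery takes, which the plan leaves open. If sites collect hCG with labs on the day of Visit 2, the age falls to 0 to 7 days.

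The absolute risk is small: at most 5 planned females, with contraception confirmed at each visit. The case rests on the fetal risk that the protocol itself states and on the low cost of the remedy. The cognitive endpoint, the secondary endpoints and their analysis are untouched. A reader might infer that the plan has no pre-dose pregnancy safeguard. It does not go that far: there is a screening test, an eligibility recheck and a contraception check.

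**What to change.** For females at Tanner stage 2 or above, keep the screening test and add one urine hCG test at Visit 2 or, preferably, at drug receipt. Testing at receipt also removes the delivery lag, which a Visit 2 test would leave at up to 7 days.

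- Record a negative result and its date before the first dose, at the receipt contact that the coordinator already makes.
- If the test is positive, hold dosing and confirm by laboratory hCG, in line with exclusion criterion 6.
- For participants under 18, apply the extension-phase rule in section 4g that results go to the parents.
- Mark the test in the Table of Remote Visits.

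The cost is one mailed kit or one local-laboratory urine test per eligible female, at most 5 as planned, plus a case report form field and a table entry. A laboratory test may mean an extra trip, because the table schedules no other lab work between screening and Visit 3. First dose may be delayed briefly. Dose, titration, study visits and analysis do not change.

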An unexpected adverse event is defined as any adverse event, the specificity or severity of which is not consistent with the risks of information described in the protocol.

Expected adverse events are those that are identified in the research protocol as having been previously associated with participation in the study.

All reported adverse events will be classified using the current version of the Common Terminology Criteria for Adverse Events (CTCAE) Version 4.0 developed and maintained by CTEP at National Cancer Institute.

Dosing: Epidiolex will be started at 5 mg/kg/day and titrated to maximum dose of 20 mg/kg/day, increasing the dose by 5 mg/kg/day weekly over the next three weeks. The investigational drug (Epidiolex/CBD) will be administered as an adjunct to all current anti-epileptic drugs.

Visit Schedule (see Figure): Subjects will be seen remotely for Screening Visit for Consent and initial studies, at Baseline Visit to start on CBD, then at 1 month, 3 months, and 6 months after initiation. Phone and/or email communication will take place bimonthly.

Lab work: CBC, chemistries including LFTs, urinalysis, Cannabidiol (CBD)/ Tetrahydrocannabidiol (THC) ratio, and trough levels of all seizure medications will be done at each visit. All labs tests will be completed remotely at an outside lab site local to the participant and charged to the study budget.

Database: A Redcap database will be used to organize data which will be analyzed with SPSS.

Method of administration: Cannabidiol oral solution 100 mg/ml will be administered orally. The participants will be treated on an outpatient basis (remotely) and will not require inpatient hospital admission.

Dose / titration schedule: Initiation of treatment will begin with 5 mg/kg/day given in two divided doses. The dose will be increased by 5 mg/kg/day after seven days and then by 5 mg/kg/day every seven days up to a maximum dose of 20 mg/kg/day given. Study drug supply will be mailed to the participants (see process outlined above). The dosing schedule will be as follows, as tolerated:

Start of study: 5 mg/kg/day; subject will be evaluated here

Week 1: Increase dose by 5 mg/kg/day for total daily dose of 10 mg/kg/day

Week 2: Increase dose by 5 mg/kg/day for total daily dose of 15 mg/kg/day

Week 3: Increase dose by 5 mg/kg/day for total daily dose of 20 mg/kg/day

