Early stopping rules: If a participant experiences a significant health decline or a loss of seizure control (defined as a need to add a new seizure medication), ending assessments will be done, and the subject removed. If the subject experiences a temporary increase in seizures, [name] may take the temporary nature of the increase into account. If the subject has had other benefits to mood, behavior, or neurologic exam that outweigh the risk of an increase in seizures, then [name] may decide to decrease the dose of the study drug since it has been observed that some subjects do well at doses lower than 20 mg/kg/day. Other removal criteria include: death, lost to follow-up, withdrawal of consent for any further data submission, or any other reason the patient, parent, PI or caring physicians think that the subject should be removed. Early withdrawals within the first two months will be replaced.

Study cessation rules. The study will be stopped if any of the following occur: (1) more than 4 subjects drop out because of adverse events probably or definitely **due to study drug** or (2) more than two subjects experience a SAE probably or definitely **due to study drug.** If any subject has a major unexpected negative event (serious injury or death) attributable to the drug, this information will be shared with the other subjects who will have the choice to come off the drug and further enrollment will cease while the event is being fully assessed.

Treatment will continue until any of the following take place:

- 1. Loss of seizure control defined as need to add another seizure medication or other seizure treatment (diet or surgery).
- 2. Intolerable toxicity.
- 3. Pregnancy.
- 4. Withdrawal of consent.
- 5. Six month treatment duration completed as per protocol.
- 6. Laboratory results indicate that the subject's liver function test (ALT or AST) has increased in any of the following ways:
 - >8xULN
 - >5xULN for more than 2 weeks
 - >3xULN and either (TBL >2xULN or INR >1.5)
 - >3xULN with the appearance of fatigue, nausea, vomiting, right upper quadrant pain or tenderness, fever, rash, and/or eosinophilia (>5%)
 - g. Description of what happens to participants receiving therapy when study ends or if a participant's participation in the study ends prematurely.

Extension Phase:

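### The liver stopping rule can turn on INR, but neither core-phase laboratory panel requires INR to be measured

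*Combined protocol and SAP*

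**What the plan says.** Section 4f lists the events that end treatment. Criterion 6 covers the liver, and for this purpose it defines the liver function test as ALT or AST. Its limbs are:

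- an elevation above 8xULN;
- an elevation above 5xULN lasting more than 2 weeks;
- the combined limb ">3xULN and either (TBL >2xULN or INR >1.5";
- a sign limb, ">3xULN with the appearance of fatigue, nausea, vomiting, right upper quadrant pain or tenderness, fever, rash, and/or eosinophilia (>5" percent.

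Two laboratory panels apply in the core phase.

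- **Scheduled labs** (Section 4a, Lab work): "CBC, chemistries including LFTs, urinalysis, Cannabidiol (CBD)/ Tetrahydrocannabidiol (THC) ratio, and trough levels of all seizure medications will be done at each visit". The visit table and item 5 under Laboratory tests and clinical procedures describe the same panel. The table adds a pregnancy test and describes the chemistry as a CMP covering renal and hepatic function.
- **Repeat and triggered labs** (Section 4b): a further draw is needed "within 72 hours of a previous blood draw if the most recent result indicates a clinically significant (>3xULN) elevation of ALT or AST". Its content is set as a floor: "At minimum, the following tests will be repeated: ALT/AST, total bilirubin, and alkaline phosphatase", with GGT added. The same tests are used for event- and symptom-triggered bloodwork: "This bloodwork (ALT/AST, total bilirubin, and alkaline phosphatase and GGT test) will also be necessary if" one of three conditions is met.

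Section 4b also provides that "All trial subjects with elevated LFTs will be followed closely until all abnormalities return to the baseline state".

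**The concern.** A mandatory stopping threshold should have a mandatory measurement behind it. INR appears once in the document, as a threshold in criterion 6, and no laboratory list names INR, prothrombin time or any coagulation test. All draws are done at outside laboratories local to the participant, so an INR exists only if someone asks for it. If the plan is followed to the letter, the combined limb shrinks to its bilirubin half.

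What is at stake is one classifying value in a subject already known to have raised enzymes. Enzyme rises are foreseeable here. Section 8a lists them among reported effects of cannabidiol, says that valproate or clobazam adds to the risk, and records a transient AST rise in 1 of the 5 earlier Sturge-Weber patients, described as indirectly related. The weekly and monthly safety reviews cannot act on a value that was never collected.

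**Working it through.** The plan gives no figure to reproduce. The check sets each quantity that criterion 6 needs against the tests the core phase requires.

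| Needed by criterion 6 | Scheduled labs (4a) | Repeat/triggered labs (4b) |
|---|---|---|
| ALT, AST | yes, as LFTs | yes, named |
| Total bilirubin | not named separately | yes, named |
| INR | no | no |

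**Could the term LFTs include INR?** The text points the other way. Criterion 6 glosses liver function test as ALT or AST. Section 4b itemises its liver panel and adds GGT, which no limb of criterion 6 uses, but leaves out INR, which one limb does.

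**Which subjects are affected?** Those who meet the INR half and no other limb. Taking the limbs in turn, all of these must hold:

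1. ALT or AST above 3xULN.
2. Not above 8xULN.
3. Not above 5xULN for more than 2 weeks.
4. Total bilirubin at or below 2xULN.
5. None of the listed signs, and no eosinophilia above 5%.
6. INR above 1.5.

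**Illustration (hypothetical values).** ALT 4xULN, bilirubin 1.5xULN, INR 1.7, and new bruising as the only sign.

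- 4 is below 8, so the first limb is not met.
- 4 is below 5, so the second limb is not met however long the elevation lasts.
- 1.5 is below 2, so the bilirubin half is not met.
- Bruising is not in the sign limb, so that limb is not met.
- 1.7 exceeds 1.5, so the INR half is met and treatment should end.

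Section 4b would bring this subject back for a draw within 72 hours, and bruising is among its symptom triggers ("fatigue, encephalopathy, nausea, vomiting, right upper quadrant pain or tenderness, abdominal pain or distension, fever, excessive bruising, excessive nose or gum bleeds, or petechia"). The required content of that draw would still not show the one value that decides the matter. While ALT stays between 3x and 5xULN, no duration limb would later end treatment either.

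**Where must INR be measured to close the gap?** INR matters to criterion 6 only once ALT or AST exceeds 3xULN, and any such result, scheduled or triggered, already leads to the 72-hour repeat. INR on that repeat draw is sufficient.

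**The case against.** The strongest reply is that the repeat panel is a stated minimum. An investigator may add INR to it, and a stopping rule that names INR can fairly be read as a prompt to obtain one when ALT or AST passes 3xULN. This stands in part: the INR half is unlisted, and it would be wrong to call it impossible to apply. But permission is not a requirement, and nothing ensures the test is ordered.

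The second reply is that other safeguards surround such a subject. They include close follow-up of raised LFTs (4b), intolerable toxicity as its own ground for ending treatment and removal at the investigator's discretion (4f), weekly safety review (7c), immediate notification of adverse events, and closer monitoring with dose reduction on valproate or clobazam (8b). Liver disease and active bleeding diathesis are excluded at entry (Section 5). All of this stands and limits the consequence. None of it supplies the INR.

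A reader might infer more than the documents support:

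- **That the gap also covers the extension phase.** Section 4g describes extension labs as clinical care, and nothing says criterion 6 carries over. The point rests on the core phase.
- **That INR is the only quantity in criterion 6 without a named test.** That would assume the CBC includes a differential for eosinophils, which the documents do not say.
- **That the bleeding signs among the Section 4b triggers reveal a separate gap.** They do not, because a resulting enzyme value above 3xULN already leads to the repeat draw.

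**Conclusion.** The point holds in limited form. Criterion 6 contains a threshold, INR above 1.5, that neither core-phase panel requires anyone to measure. The bilirubin half of the same limb is covered. A subject who qualifies only through INR could remain on drug unless a clinician orders an unlisted test or stops treatment on other grounds.

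It would be a mistake to conclude that liver injury would go unnoticed. The enzyme elevation is detected, repeated within 72 hours and followed. What may be missing is the value that makes stopping mandatory.

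The likelihood of an INR-only case among 10 subjects is unknown, and the documents offer nothing from which to estimate it. The conclusion assumes only that LFTs and the hepatic part of the CMP do not include INR, which the wording of 4b and 4f supports. There is no bearing on the cognitive outcome or its analysis. Severity is minor. The absence of the test from the lists is certain; its practical consequence is not.

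**What to change.** In Section 4b, add PT/INR to the tests required on the repeat draw within 72 hours of an ALT or AST result above 3xULN. Leave the INR limb of criterion 6 in Section 4f as it is. Because draws are ordered from local laboratories, the prescription for the repeat draw should name PT/INR.

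The cost is one extra assay on each such repeat draw, plus a one-line wording change. No extra draw or visit is needed. PT/INR need not be added to all event- or symptom-triggered bloodwork, since any result there above 3xULN already leads to the repeat draw.
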